## **2.2.4 Exploratory Endpoint**

The exploratory endpoint of this trial is EEG (optional assessment).

## **2.3 Overall Study Design**

This is a multicentre, double-blind, randomised, placebo-controlled, parallel-group trial in patients at high risk of developing unprovoked seizures after acute intracerebral haemorrhage or an acute ischaemic stroke.

At the first visit (screening/baseline, V1a), patients will undergo several examinations to check eligibility. The next visit (V1b) has to be performed within 120 hours after primary stroke occurrence or since last time seen well. After eligibility has been confirmed, patients will be randomised to treatment with ESL 800 mg or placebo.

Patients will start treatment with the investigational medicinal product (IMP) i.e. ESL or placebo within 120 hours after primary stroke occurrence, or since last time seen well at V1b. They will continue treatment until Day 30 after randomisation and then be tapered off. Thereafter, patients will be followed up until 18 months after randomisation.

If one or more AS(s) occur(s) within 7 days after primary stroke, this will not result in change of IMP dose. Patients having a first US will discontinue IMP treatment and will be treated at the discretion of the investigator until 18 months after randomisation, except with commercially available ESL.

## **2.4 Randomisation**

After confirmed eligibility at V1b, patients will be randomised (randomisation ratio 1:1) to treatment with ESL 800 mg or placebo.

## 2.5 Treatments

Treatment name	Dosage Form	Active ingredient	Strength/concentration
ESL	Tablet	Eslicarbazepine acetate (ESL)	800 mg
Placebo	Tablet	None	Not applicable

Treatment with IMP will start at V1b (i.e. within 120 hours after primary stroke, or since last time seen well) and will be continued for 30 days. Thereafter, the IMP will be tapered off, as applicable. The dosing will be as follows:

Patients with an eGFR  $> 60$  mL/min/1.73 m^2 will take one tablet once daily (800 mg ESL or placebo). Patients with moderate renal impairment at V1a, defined as eGFR 30 – 60 mL/min/1.73 m^2, will take half a tablet once daily (400 mg ESL or placebo). As soon as eGFR has improved to  $> 60$  mL/min/1.73 m^2, the dose will be increased to one tablet once daily (800 mg ESL or placebo). Patients developing moderate renal impairment during IMP intake should be adjusted to 400 mg, if applicable. Worsening of renal function with an eGFR  $< 30$  mL/min/1.73 m^2 must lead to discontinuation of IMP intake (dose independent) without down-titration.

Patients taking one tablet once daily (800 mg ESL or placebo) must be down-titrated for 7 days before stopping intake of IMP i.e. those patients will take half a tablet (400 mg ESL or placebo) from Day 31 to Day 37. Patients taking half a tablet once daily (400 mg ESL or placebo) on Day 30 do not require down-titration i.e. they will take the last IMP on Day 30.

## 2.6 Sample Size

Based on retrospective historical data, 26% of patients are expected to experience the first US (i.e. failure rate) within the first 6 months after stroke with standard of care. As this is a pilot trial, no empirical estimate of the treatment effect in patients randomised to ESL is available. For the purpose of sample size estimation, the trial is planned to have at least 80% power to demonstrate a significantly lower failure rate under ESL compared to placebo under the following assumptions:

- An expected failure rate (including death and other reasons of missing data before the first US) of 26% under placebo within the first 6 months after stroke
- An expected failure rate (including death and other reasons of missing data before the first US) of 8% under ESL within the first 6 months after stroke

Under these assumptions 100 randomised patients per treatment arm will ensure a power of the trial of at least 80% to demonstrate a significantly lower failure rate under ESL compared to placebo by means of a two-sided chi-square test on a 5%-level of significance.

Recruitment was terminated before reaching the estimated sample size.

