14. ECG
15. Suicidal ideation and behaviour (as per PHQ-9, question 9)

Exploratory endpoint:

16. EEG, optional

Statistical methods:**Analysis sets:**

- Enrolled set (ES): All patients enrolled into this trial.
- Safety set (SS): All patients who were randomised and were treated with at least one dose of IMP (ESL or placebo). Patients will be assigned to treatment groups as treated.
- Full analysis set (FAS): All patients who were randomised and were treated with at least one dose of IMP (ESL or placebo). Patients will be assigned to treatment groups as randomised.
- Per protocol set (PPS): All patients of the FAS without major protocol deviations. Patients will be assigned to treatment groups as treated.
- EEG analysis subset: All patients in the FAS with a baseline and a post-baseline EEG recording available.

The primary hypotheses will be assessed in the FAS by means of a chi-square test with continuity correction on the significance level of 5% (two-sided).

Secondary efficacy analysis includes an analysis of the proportion of patients who experience the first US within the first 12 and within 18 months after randomisation (12 months and 18 months failure rate, respectively), time to first US after randomisation as well as time to first US after stroke by means of Kaplan-Meier estimate, and cause-specific cumulative incidence curves to evaluate the competing risk in case of deaths before the first US, as well as descriptive statistics for number of AEs, number and 4-week rate of USs, the BI, the NIHSS score, the PHQ-9.

EEG parameters will be evaluated exploratively using descriptive statistics.

Safety analysis will focus on the presentation of TEAEs by system organ class (SOC) and preferred term (PT), and the analysis of vital signs, safety laboratory data, ECG, physical and neurological examination, and suicidal behaviours assessed using PHQ-9.

Sample size estimation: Based on historical data, 26% of patients are expected to experience the first US within the first 6 months after stroke (i.e. failure rate) with standard of care. As this is a pilot trial, no empirical estimate of the treatment effect in patients randomised to ESL is available. For the purpose of sample size estimation, the trial is planned to have at least 80% power to demonstrate a significantly lower failure rate under ESL (Group A) compared to placebo (Group B) under the following assumptions:

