- An expected failure rate (including death before the first US) of 26% under placebo within the first 6 months after stroke.
- An expected failure rate (including death before the first US) of 8% under ESL within the first 6 months after stroke.
- In order to account for a missing data rate of 5% for reasons other than death before the first US, in each treatment arm, the sample size calculated on adjusted failure rates (including missing data) of 29.7% under placebo and 12.6% under ESL, respectively.

Under these assumptions 100 randomised patients per treatment arm will ensure a power of the trial of at least 80% to demonstrate a significantly lower failure rate under ESL compared

to placebo by means of a two-sided chi-square test with continuity correction on a 5%-level of significance.

Assuming that the failure rate in missing observations equals the failure rate with placebo for both treatment groups, the power of the trial is 87%. Based on the expected failure rates without adjustment for missing data, the power of the trial is 89%.

Schedule of trial procedures

Visits	V1a ²	V1b ²	V2 ¹⁵	V3 ¹⁵	V4	V5	V6	V7	V8	EoT ¹²	EDV ³	UNS ¹
Days / Weeks after V1b			+7 days	+37 days	+12 weeks	+26 weeks	+38 weeks	+52 weeks	+64 weeks	+78 weeks		
On-site visit ☺/telephone contact ☎	☺	☺	☺	☺	☎	☺	☎	☺	☎	☺	☺	☺/☎
Day	-3 to -1	1 (within 96 h after stroke)	8±2	38±4	85±10	183±10	267±10	365±10	449±10	547±10		
Initiation procedures												
Informed consent	● ⁹			● ¹⁰							(●) ¹⁴	
Demographics	●											
Medical history	●			● ¹⁰							(●) ¹⁴	
Prior medication	●			● ¹⁰							(●) ¹⁴	
Concomitant medication	●	●	●	●	●	●	●	●	●	●	●	●
SeLECT score/CAVE score ¹¹	● ⁴											
Modified Rankin Scale (mRS)	● ⁴											
Inclusion/exclusion criteria	●	●	● ¹⁰									
Randomisation (1:1)		●										
Medication												
First investigational medicinal product (IMP) administration		●										
Dispense IMP		●									(●)	
IMP accountability				●							● ¹³	(●)
Efficacy												
Issue diary (seizures)	●		●	●		●		●			(●)	
Review and collect diary		● ⁸	●	●		●		●		●	●	(●)
Seizure screening questionnaire	●	●	●	●	●	●	●	●	●	●	●	●
Record seizures (diary/questionnaire) ¹⁶	●	●	●	●	●	●	●	●	●	●	●	●
Barthel Index (BI)	●			●		●		●		●	●	(●)
National Institutes of Health Stroke Scale (NIHSS)	● ⁴		●	●		●		●		●	●	(●)
Patient Health Questionnaire (PHQ-9)	●			●		●		●		●	●	(●)
Electroencephalogram (EEG, optional) ⁵	(● ⁴)									(●)		(●)

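### Do the 26% and 8% failure rates in SAP 2.6 fail to support 100 patients per arm and at least 80% power?

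*SAP*

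**What the plan says.** SAP section 2.6 opens with historical data: "26% of patients are expected to experience the first US (i.e. failure rate) within the first 6 months after stroke" under standard of care. Its first planning assumption reuses the figure as "An expected failure rate (including death and other reasons of missing data before the first US) of 26% under placebo", and the second gives 8% for eslicarbazepine acetate (ESL) under the same wide label. From these it states 100 randomised patients per arm and a power of 80% or more, with a two-sided 5% chi-square test and no mention of a continuity correction. It closes by noting that recruitment ended short of the planned number.

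The protocol synopsis (Sample size estimation) uses the same two percentages differently. Its historical sentence reads "26% of patients are expected to experience the first US within the first 6 months after stroke (i.e. failure rate", and its assumption reads "An expected failure rate (including death before the first US) of 26% under placebo within the first 6 months after stroke", so there 26% covers death but not other missing data. It then adds a step: "In order to account for a missing data rate of 5% for reasons other than death before the first US", with "the sample size calculated on adjusted failure rates (including missing data) of 29.7% under placebo and 12.6% under ESL". From those rates, and with the continuity correction named, it reaches 100 per arm and 80% or more. It gives two further figures for the same trial: "equals the failure rate with placebo for both treatment groups, the power of the trial is 87" per cent, and "Based on the expected failure rates without adjustment for missing data, the power of the trial is 89" per cent.

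SAP section 5.5.1 sets the primary test as the chi-square test with continuity correction. SAP section 8, which lists changes from the protocol, says nothing about the sample-size text.

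**The concern.** Three things look wrong. First, 26% cannot be both the rate of a first US alone and the rate of US, death and missing data together, unless deaths and dropouts are nil. The primary endpoint counts all three as failures (SAP 2.2.1), so the two readings imply different planned effects. Second, 100 per arm does not come out of 26% versus 8% at 80% power. The SAP seems to join the inputs of the synopsis's 89% case to the size and power of its 80% case. Third, section 2.6 describes a slightly different test from section 5.5.1.

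At stake would be the traceability of the planning basis. A reader who recomputes section 2.6 finds a trial powered near 90%, not one sized at 80%. Because recruitment stopped early, that reader may want the planning assumptions when interpreting a non-significant result.

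**Working it through.** **Inputs.** SAP 2.6: 26% versus 8%, 100 per arm, two-sided 5%. SAP 2.4: 1:1 allocation. Synopsis: 5% missing per arm, 29.7% versus 12.6%, continuity correction, and power of 80% or more, 87% and 89%.

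**Formulas.** With d = p1 − p2 and p̄ = (p1 + p2)/2, the uncorrected size per arm is

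n = [1.96·√(2p̄(1 − p̄)) + 0.842·√(p1(1 − p1) + p2(1 − p2))]² / d².

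The continuity-corrected size is n_cc = (n/4)·[1 + √(1 + 4/(n·d))]². For corrected power at 100 per arm, use an effective size of (100 − 1/d)²/100 in the uncorrected power formula. Exact power sums the two binomial distributions over all tables that the test rejects.

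**The synopsis's own figures**

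- Missing counted as failure: 0.26 + 0.05 × 0.74 = 0.297 and 0.08 + 0.05 × 0.92 = 0.126. Both match.
- 29.7% versus 12.6%: d = 0.171, p̄ = 0.2115, n = (1.132 + 0.475)²/0.171² = 88.3, n_cc = 99.7. This gives 100 per arm. Corrected power at 100 is 80.1% by formula and 80.9% exact.
- Missing patients failing at the placebo rate: ESL becomes 0.95 × 0.08 + 0.05 × 0.26 = 0.089. Corrected power for 26% versus 8.9% is 85.7% by formula and 86.6% exact, against 87% printed.
- 26% versus 8% unadjusted: 89.9% by formula and 90.9% exact, against 89% printed.

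The synopsis is therefore coherent to within about 2 points.

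**SAP 2.6 as written**

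For 26% versus 8%, d = 0.18 and p̄ = 0.17, so n = (1.041 + 0.434)²/0.18² = 67.2 and n_cc = 77.9. A power of 80% needs 68 per arm without the correction and 78 with it.

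| Test at 100 per arm, 26% vs 8% | Formula | Exact |
|---|---|---|
| With continuity correction | 89.9% | 90.9% |
| Without | 92.9% | 94.1% |

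Every entry is above 80%. The section gives a lower bound, and the bound holds whichever test is meant. What is lost is the route by which 100 was chosen.

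**Size of the labelling difference.** If the 26% and 8% already contain a missing share m, the implied rate of US or death is (f − m)/(1 − m). The SAP gives no m. Assuming 1%, 3% or 5% (the last being the synopsis figure), the implied rates are 25.3%/7.1%, 23.7%/5.2% or 22.1%/3.2%. These are relative reductions of 72%, 78% or 86%, against 1 − 8/26 = 69% for the rates as printed. The label therefore changes how large an effect the planners appear to have assumed. It does not change the power of the test on the composite endpoint, which depends only on the two failure rates.

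**The case for a change.** The strongest case for acting is that two of the defects need no other document: the double meaning of 26% and the missing mention of the correction both stand within the SAP. A planning paragraph should let the reader say what effect was assumed, and here the answer could be a relative reduction of anywhere from 69% to 86%. The trial also stopped early, and planned power at a smaller size depends on which rates are taken. At an assumed 60 per arm, exact corrected power is 69% for 26% versus 8% and 55% for 29.7% versus 12.6%. If the paragraph departs from the governing protocol, section 8 ought to say so. A correction would cost a few words.

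The labelling faults stand as described; the consequences do not.

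- The wider label in the assumptions is the one that fits the endpoint, which counts dropouts for any reason as failures. The odd one out is the background sentence on historical data, and its blurring of US with US or death is already in the synopsis.
- The synopsis applies 26% versus 8% to 100 per arm in its 89% case, so that pairing is not foreign to the protocol. The SAP quotes a looser bound for it.
- The SAP covers protocol version 3.0, with a 120-hour window, and states that its statistical considerations amend the protocol. Without the version 3.0 text, an omission from section 8 cannot be shown.
- A non-significant result will be read from the risk difference with its Newcombe interval and from the odds ratio interval (SAP 5.5.1), not from planning power. The final size is not given, so power at smaller sizes is hypothetical.

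**Conclusion.** The plan does not need to change. Section 2.6 is loosely worded: 26% is given two meanings, a derivation step present in the synopsis is absent, and the correction is not named. But the power it claims is met on its own rates by about 10 to 14 points (89.9% to 94.1% against 80%). The primary test is settled in section 5.5.1, so an analyst has no choice to make about the correction. No dataset, test or estimate draws on section 2.6, and recruitment has ended, so the planned size can no longer be altered. Rewording would make the paragraph easier to trace but would change no result and no conclusion.

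This rests on taking 26% and 8% as rates of the composite failure endpoint, as the SAP's two assumptions do, and on 1:1 allocation at 100 per arm. Whether the SAP departs from the governing protocol on this paragraph stays open, because the only sample-size text to compare has the earlier 96-hour window. A departure would be a matter of record-keeping and would leave the analysis as it is.

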## 2.7 Blinding

ESL and placebo tablets will be identical in size, colour, taste and appearance. The packaging and labelling will not allow for any distinction between test drug and placebo.

No person involved in conducting the trial may have access to the randomisation code before the blind is officially broken.

### **3. ANALYSIS SETS AND SUBGROUPS**

#### **3.1 Analysis Sets**

The **Enrolled Set** (ES) will be defined as all patients who have been enrolled in the trial (i.e. informed consent form (ICF) signed by patient, by witness in case of verbal consent or by patient's legal representative or deferral of informed consent adequately documented and signed by the investigator).

The **Randomised Set** (RS) will be defined as all patients who were randomised.

The **Safety Set** (SS) will be defined as all patients who were randomised and were treated with at least one dose of IMP (ESL or placebo). Patients will be assigned to treatment groups as treated.

The **Full Analysis Set** (FAS) will be defined as all patients who were randomised and were treated with at least one dose of IMP (ESL or placebo). Patients will be assigned to treatment groups as randomised.

The **Per-Protocol Set** (PPS) will be defined as all patients of the FAS without any major protocol deviations and with verbal witnessed or signed written consent. Patients will be assigned to treatment groups as randomised.

The **EEG analysis subset** will be defined and described in the separate EEG report.

#### **3.2 Subgroups**

For analysis of efficacy endpoints the following subgroups will be defined based on:

1. Acute intracerebral haemorrhagic stroke versus acute ischemic stroke
2. Time of treatment start (treatment start within the first 72 hours after primary stroke vs. treatment start after 72 hours after primary stroke). In case of unknown start time of IMP, it will be assumed that first IMP intake was at 23:59.

Exploratory subgroup analysis of unprovoked seizures only at 18 months will be performed in the FAS.

Final decision concerning subgroup analyses and definitions were made during Blind Data Review (BDR).

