### **4.1 General Methodology and Presentation of the Results**

The default summary statistics for quantitative (continuous) variables will be

- the number of patients with data at the visit (n),
- number of patients with missing data (nmiss),
- mean,
- standard deviation (SD),
- median,
- first quartile (Q1) and third quartile (Q3)
- minimum (min) and maximum (max)

for patients with data.

Mean, median, and the quartiles will be presented to one more decimal place than the raw value. The minimum and maximum values will be presented with the same decimal precision as the raw value. SD will be reported to two decimal places greater than the original value.

For qualitative (categorical) variables, the number (n) and percentage (%) of patients with non-missing data per category will be the default frequency tabulations. Where appropriate and present, the number of missing values will be displayed as “Missing” category.

Percentage values are to be presented to one decimal place, for example, 52.3%.

The denominator used for calculation of the percentages will be specified in a footnote to the tables for clarification.

All reported p-values will be two-sided. No adjustment for multiplicity will be performed.

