### **5.5 Efficacy Analysis**

#### **5.5.1 Primary Efficacy Analysis**

The FAS and the PPS will be used for the analysis of the primary efficacy analysis.

The primary endpoint is the proportion of patients who experience the first US within the first 6 months (until Day 182) after randomisation (failure rate). First US within the first 6 month, deaths before the first US and patients without evaluable assessment of the primary endpoint will be counted as treatment failures. The first occurring event will be used for this analysis e.g. if a patient experiences an US and dies later, this patient will be included as a patient with an US. If a patient experienced a re-stroke, the patient will be counted as a withdrawal with the date of re-stroke as ‘Date of withdrawal’.

To show that ESL is different to placebo, the primary null hypothesis

$$H_0: p_{ESL} \geq p_{placebo}$$

will be tested against the alternative hypothesis

$$H_1: p_{ESL} < p_{placebo}$$

where  $p_{ESL}$  and  $p_{placebo}$  denote the proportions of patients with the first US within 6 months after randomisation in ESL and placebo patients, respectively.

The primary hypotheses will be assessed in the FAS by means of a chi-square test with continuity correction on the significance level of 5% (two-sided, which corresponds to the significance level of

2.5% one-sided). The Odds Ratio for Placebo vs. ESL and the corresponding 95% score CI will be provided. The Risk Difference (RD) of failing between Placebo and ESL with corresponding 95% continuity-corrected Newcombe Confidence Interval (CI) for the risk difference Placebo – ESL will be calculated. Additionally, the p-value of Fisher's exact test will be provided.

For this purpose, the following SAS code will be used:

**Note: Data should be sorted by descending treatment group (first “ESL” then “Placebo”) and by treatment failures (first “Failure” then “Non-failure”).**

```
PROC FREQ DATA = <dataset> order=data;
  TABLE <Treatment group> * < Treatment Failure>
    /CHISQ RISKDIFF (CL =Newcombe (Corrected)) OR(CL =SCORE) ALPHA=0.05;
RUN;

PROC FREQ DATA = <dataset> order=data;
  tables <Treatment group> * < Treatment Failure>/ fisher;
run;
```

The following statistical outputs will be created:

Table 15.2.1.1.1 Analysis of Treatment Failure Rate within 6 Months after Randomisation – Full Analysis Set

Table 15.2.1.1.2 Analysis of Treatment Failure Rate within 6 Months after Randomisation – Per-Protocol Set

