Degrees of freedom (DF), value and p-value for chi-square test, RD of failing between ESL and Placebo with corresponding 95% continuity-corrected Newcombe CI as well as ESL vs Placebo OR with 95% score confidence interval will be presented for all possible combinations of imputed non-failures in ESL and Placebo arm.

Table 15.2.1.5.1 Sensitivity Analysis of Unprovoked Seizures within 6 Months after Randomisation – Full Analysis Set

Table 15.2.1.5.2 Sensitivity Analysis of Unprovoked Seizures within 6 Months after Randomisation – Per-Protocol Set

Table 15.2.1.5.3 Sensitivity Analysis of Unprovoked Seizures within 12 Months after Randomisation – Full Analysis Set

Table 15.2.1.5.4 Sensitivity Analysis of Unprovoked Seizures within 12 Months after Randomisation – Per-Protocol Set

Table 15.2.1.5.5 Sensitivity Analysis of Unprovoked Seizures within 18 Months after Randomisation – Full Analysis Set

Table 15.2.1.5.6 Sensitivity Analysis of Unprovoked Seizures within 18 Months after Randomisation – Per-Protocol Set

Table 15.2.1.5.7 Sensitivity Analysis of Unprovoked Seizures within 18 Months after Randomisation (Subgroup 1) – Full Analysis Set

Table 15.2.1.5.8 Sensitivity Analysis of Unprovoked Seizures within 18 Months after Randomisation (Subgroup 2) – Full Analysis Set

Number and percentage of unprovoked seizures and non-failures 6, 12 or 18 months after randomisation will be tabulated, including degrees of freedom (DF), value and p-value for chi-square test, p-value for Fisher's exact test, RD of failing between ESL and Placebo with corresponding 95% continuity-corrected Newcombe CI as well as ESL vs Placebo OR with 95% score confidence interval.

Figure 15.2.1.1.1 Tipping Point Analysis of Treatment Failure Rate within 6 Months after Randomisation – Full Analysis Set

Figure 15.2.1.1.2 Tipping Point Analysis of Treatment Failure Rate within 6 Months after Randomisation – Per-Protocol Set

Results (p-values) of the tipping point analysis will be presented via heatmap.

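### The two 18-month subgroup tables plan ESL-versus-placebo tests but no comparison of the treatment effect between subgroup levels

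*SAP*

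**What the plan says.** SAP 3.2 names two factors: haemorrhagic versus ischaemic stroke, and first IMP intake within versus after 72 hours of the primary stroke. The analysis is limited in scope: "Exploratory subgroup analysis of unprovoked seizures only at 18 months will be performed in the FAS".

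The outputs are Tables 15.2.1.5.7 (Subgroup 1) and 15.2.1.5.8 (Subgroup 2) in SAP 5.5.1.1. They share one description with six whole-population tables. It lists "p-value for chi-square test, p-value for Fisher's exact test, RD of failing between ESL and Placebo", with a continuity-corrected Newcombe interval for the risk difference and an odds ratio with a score interval. All of these compare ESL with placebo. In this analysis only an observed unprovoked seizure counts as a failure; deaths, withdrawals and missing data count as non-failures.

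The test comes from SAP 5.5.1: "chi-square test with continuity correction on the significance level of 5% (two-sided, which corresponds" to 2.5% one-sided. SAP 4.1 adds: "All reported p-values will be two-sided. No adjustment for multiplicity will be performed". Neither the protocol synopsis nor the SAP mentions an interaction test, a homogeneity test across levels, or any other between-level comparison.

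**The concern.** Splitting patients by stroke type or by start time asks whether the effect of ESL differs between the levels. A p-value within one level answers another question: whether there is evidence of an effect in that level alone. It depends on the number of patients and events in the level as well as on the size of the effect. One level can be significant and the other not simply because the second is smaller, or by chance when both have moderate power.

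At stake is a reading such as benefit in one stroke type only, or benefit only with an early start. The planned tables would contain the p-values that invite this reading but no statistic that tests it.

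**Working it through.** **Inputs.** The protocol synopsis, under sample size estimation, assumes for the control arm: "An expected failure rate (including death before the first US) of 26% under placebo within the first 6 months after stroke". On the same definition, the rate assumed with ESL is 8%. The calculation then allows for a "missing data rate of 5% for reasons other than death before the first US". The test is the continuity-corrected chi-square at two-sided 5%, with 1:1 allocation. The documents give no final sample size, no subgroup splits and no expected 18-month seizure-only rate, so the sample sizes and splits below are assumptions.

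**Step 1: reproduce the plan's own figure.** Counting 5% missing as failures gives 0.95 × 26% + 5% = 29.7% and 0.95 × 8% + 5% = 12.6%, as the protocol states. With mean rate p̄ = 0.2115 and difference d = 0.171, the uncorrected sample size is

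n₀ = [1.96·√(2p̄(1−p̄)) + 0.842·√(p₁(1−p₁) + p₂(1−p₂))]² / d² = 88.3.

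With continuity correction, n = (n₀/4)·[1 + √(1 + 4/(n₀d))]² = 99.7, so 100 per arm. Exact enumeration of the corrected test at 100 per arm gives 80.9% power. This agrees with the protocol: "Under these assumptions 100 randomised patients per treatment arm will ensure a power of the trial of at least 80"%.

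**Step 2: same true effect in both levels.** Let A and B be the exact powers of the corrected chi-square in the two levels. Then

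P(exactly one level has p<0.05) = A(1−B) + B(1−A).

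At 29.7% vs 12.6% in both levels:

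| Per arm, level 1 + level 2 | A | B | Exactly one significant |
|---|---|---|---|
| 50 + 50 | 0.472 | 0.472 | 49.8% |
| 70 + 30 | 0.629 | 0.259 | 56.2% |
| 45 + 20 | 0.409 | 0.153 | 43.7% |
| 25 + 25 | 0.185 | 0.185 | 30.2% |
| 35 + 15 | 0.318 | 0.077 | 34.6% |
| 15 + 15 | 0.077 | 0.077 | 14.2% |

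For 70 + 30, for example: 0.629 × 0.741 + 0.259 × 0.371 = 0.466 + 0.096 = 0.562. Of the 56.2 percentage points, 46.6 are the pattern in which the larger level is significant and the smaller is not.

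**Step 3: vary the rates.**

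- 26% vs 8%: 48.5% (50 + 50), 59.4% (70 + 30), 51.1% (45 + 20).
- 20% vs 10% (assumed): 31% (50 + 50), 20% (45 + 20), 12% (25 + 25).
- 15% vs 8% (assumed): 19% (50 + 50), 6% (25 + 25).
- No effect, 26% or 17% in both arms: 5-6% (50 + 50), 3-4% (25 + 25).

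**Step 4: what an interaction test would do.** A Wald test on the difference in log odds ratios was simulated (0.5 added to each cell, 200,000 runs). With an identical 26% vs 8% effect in both levels, it declared the effects different in 2.7-2.8% of trials at 200 patients in total and about 1% at 60. With 26% in all arms, the rate was 1.7-4.7%.

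**The case against.** The analysis is labelled exploratory, sits in a trial that the SAP calls a pilot, and was narrowed to one endpoint at one time point. No section says that significance in one level will support a claim of differing effects. The table shells are separate attachments, so one set of p-values per level is inferred from a description shared by eight tables. All of this stands. It limits the consequence, but it does not make within-level p-values answer the between-level question.

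A reader might infer from Step 2 that identical effects would look different about half the time in this trial. The documents do not support that. The figure needs a real effect of about the planned size and roughly 130 to 200 patients, and SAP 2.6 says recruitment ended before the target was reached. The rates also belong to another endpoint: a 6-month composite in which deaths and missing data are failures. The subgroup endpoint counts those as non-failures but runs to 18 months. These two differences pull in opposite directions, so the direction of the error is unknown. In small subgroups the usual result is that neither level is significant (85% of trials at 15 + 15), which does not invite a one-level claim.

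Part of the obvious remedy is already planned: the effect estimates with intervals and the exploratory label. Removing the within-level p-values would be a preference, since an interaction estimate can be added without it.

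**Conclusion.** The gap is real and minor. The two subgroup tables plan tests of ESL against placebo and no comparison of the effect between levels, so those tests cannot show whether the effect differs by stroke type or by start time.

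The size of the risk is conditional. The illustration ranges from about 14% at 30 per arm to 50-56% at 100 per arm, and falls to about 3-6% with no effect. It assumes the same control rate and the same effect in both levels, 6-month composite rates standing in for 18-month seizure-only rates, and illustrative sample sizes and splits. It shows how the artefact arises; it does not predict how often it would occur here. That the within-level p-values will be used to claim a differing effect is also only something a reader might infer, since no section says so.

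**What to change.** In each of Tables 15.2.1.5.7 and 15.2.1.5.8, keep the planned risk difference and odds ratio with 95% CI for each level. Add one treatment-by-subgroup interaction estimate, either the ratio of odds ratios or the difference in risk differences, with 95% CI and p-value. Use an exact homogeneity test if events are sparse. Label it exploratory, and state in SAP 3.2 that any statement about differing effects will rest on this estimate and not on the within-level p-values.

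The cost is one added statistic per table and one sentence in the SAP; no new data are needed. The downside is low power: a non-significant interaction will not show that the effects are equal, and the table footnote should say so.
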